9.1. Trial treatments

Six cycles of 28 days each:

Arm A: Triptorelin 3.75 mg i.m. on day 1 of every cycle + letrozole 2.5 mg/day orally for 6 cycles

Arm B: Degarelix 240 mg s.c. given as two subcutaneous injections of 120 mg on day 1 of cycle 1, followed by 80 mg s.c. on day 1 of cycles 2 to 6 + letrozole 2.5 mg/day orally for 6 cycles

Letrozole 2.5 mg/day orally should be started on day 1, concurrently with triptorelin or degarelix.

Trial treatment should start as soon as possible, and no later than 14 days after randomization.

NOTE: Treatment can be started at any time during the menstrual cycle.

Trial treatment stops at surgery.

If the patient has to continue endocrine treatment with an LHRH analogue after surgery, she should wait at least 6 weeks from the date of last administration of degarelix in order to avoid drug interactions.

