10.1. Tumor measurements

Bilateral mammography and breast ultrasound are required at baseline, after 3 treatment cycles and prior to surgery.

Breast ultrasound and mammography are mandatory.

The technique(s) used for measurement of the tumor will be left to the discretion of the Investigator, however, for each patient the same technique(s) should be used throughout the study treatment period. Whenever possible, measurements should be made by the same Investigator or reporter for all assessments for each patient.

All measurements (bi-dimensional) should be recorded in metric notations (centimeters and tenths of centimeters) using a ruler or calipers.

In the case of multifocal or multicentric disease, only the lesion with the largest dimensions will be considered.

Primary tumor diameters as well as nodal status must be reported in the appropriate sections of the eCRF.

All measurable lesions with diameter(s) that decrease to < 0.5 cm will continue to be recorded as having a diameter of 0.5 cm until the lesion is completely resolved or until the diameter increases to > 0.5 cm. When the diameter increases to > 0.5 cm, the actual measured diameter will again be recorded. When the lesion is completely resolved, record as: 0.0 x 0.0 cm.

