10.3. Best overall response

Best overall response is defined as best response recorded from the start of treatment across all time points until disease progression. Confirmation of partial or complete response by an additional scan is not requested in this trial. Best overall response will be determined by a team consisting of the Study Chair, Co-chair and IBCSG Head of Medical Affairs.

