1.4 TRIAL CONDUCT

1.4.1 Protocol Versions/Amendments

The trial was activated with protocol version 1.0 on dated 28 March 2013, and first patient enrolled on 24 February 2014. Final patient enrolled in January 2017 with final enrollment of N=51.

There is no amendment.

1.4.2

IBCSG Data and Safety Monitoring Committee (DSMC) conducts regularly scheduled semi-annual reviews of interim clinical and safety data for trial 41-13 (TREND)

The DSMC conducted reviews on April 24, 2014 and subsequently around every 6 month, concluded the trial to continue as planned.

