2.2.4 Secondary Endpoints

1. Node-negative disease at surgery: The number of lymph nodes assessed at surgery minus the number of positive nodes identified, equal to zero.
2. Breast-conserving surgery (BCS): Whether or not patient undergoes BCS (per Surgery form). If patient does not undergo surgery within the trial then patient is to be excluded from the surgery outcome summary (analysis is based on surgery population)
3. Change in Ki67 expression level: the percent change in Ki67 expression from pre-treatment diagnostic (baseline) biopsy to surgery, calculated as (surgery-baseline)/baseline*100.
4. The Preoperative Endocrine Prognostic Index (PEPI, range 0-12) score at time of surgery: By integrating central pathology review (CPR) results of pathological features and biomarkers with risk points (table below), the PEPI is the sum of the risk points with a 0 score representing the best prognostic feature, as previously determined to be associated with recurrence-free survival (RFS):

Pathology, biomarker status	RFS	
	HR	Adverse Points
Tumor size:		
T1/2		0
T3/4	2.8	3
Nodal status		
Negative		0
Positive	3.2	3
Ki67 level		
0 – 2.7% (0 – 1 ^a)		0
>2.7 – 7.3% (1 – 2 ^a)	1.3	1

>7.3 – 19.7%	(2 – 3 ^a)	1.7	1
>19.7 – 53.1%	(3 – 4 ^a)	2.2	2
>53.1%	(>4 ^a)	2.9	3
ER status, Allred score			
0 – 2		2.8	3
3 – 8			0

^aThe natural logarithm interval corresponding to the per cent Ki67 values on the original percentage scale

5. Best overall response: based on WHO tumor measurement and response criteria [1], measured from the start of treatment across all time points until disease progression or the end of 6 cycles of neoadjuvant therapies, whichever comes first. Response was determined by the IBCSG Head of Medical Affairs. An internal review (IR) form was created to record the final determination on best overall response. Confirmation of partial or complete response by an additional scan was not required in this trial.

Best overall response was assessed based on changes in tumor size from baseline to the assessments after 3 and after 6 cycles (denoted as day 1 of cycle 4 and prior to surgery respectively) as measured physically by caliper or ruler and as measured by breast tumor imaging (i.e., bilateral mammography and breast ultrasound).

- Complete Response (CR): The disappearance of all known disease;

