The PRS were assessed using the Functional Assessment of Cancer Therapy Endocrine Subscale (FACT-ES: for endocrine symptom) comprising 19 items (each has score range from 0 to 4) with a possible maximum total score (denoted as ESS) of 76. Functional Assessment of Chronic Illness Therapy (FACIT) guidelines will be used for scoring and interpretation of the FACT-ES total score.

The primary endpoint was FACT-ES total score (or ESS). Note that the FACT-ES items are negatively framed, thus scores were reversed for analysis so that high scores equate to a good quality of life (QOL) [Lesley et al]

In order to better describe the specific type of QOL measures, as exploratory analysis, four subscales/groups of FACT-ES were also summarized, namely,

- Vasomotor symptoms (VS, score 0-12): hot flashes, cold sweats, night sweat (note: sleeping difficult was an item not collected in our dataset)
- Neuropsychological symptoms (NS, score 0-16): light-headed/dizzy, headache, mood swings, feeling irritable (lack of energy, nervous were not collected in our study)
- GI symptoms (GIS, score 0-16): Vomiting, Gained weight, Diarrhea, bloated feeling (nausea no data)
- Gynecologic symptoms (GYNS, score 0-28): vaginal discharge, vaginal irritation, vaginal bleeding, vaginal dryness, discomfort intercourse, lost interest in sex, breast tenderness

To provide clinically useful information regarding treatment side effects, patient responses to each ES question are labeled as “clinically significant” if they scored 3 or 4 (corresponding to “quite a bit” or “very much” a problem, respectively, on the questionnaire) and as “not clinically significant” for scores of 0, 1, or 2 (“not at all”, “a little bit”, or “somewhat” a problem, respectively). The questionnaire is completed before any subsequent procedures or treatment and refers to the past 7 days.

All patients who received at least one dose of study treatment and with at least one FACT-ES assessment were included in the analysis (PRS population=ITT population).

The differences in FACT-ES scores (ESS) measurements between the two treatment arms over time were assessed using a mixed-effect model (SAS proc mixed, note a change from GEE model stated in the protocol, due to the small sample size and for simplicity). The ESS

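### Best overall response was determined by one person in the SAP but by a three-role team in the protocol, with no masking described and no rule for discordant measurements

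*SAP*

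**What the plan says.** **Who decides.** Protocol 10.3 states: "Best overall response will be determined by a team consisting of the Study Chair, Co-chair and IBCSG Head of Medical Affairs". The synopsis (Protocol 1) and Protocol 4.2 say the same. SAP 2.2.4 item 5 states: "Response was determined by the IBCSG Head of Medical Affairs", and adds: "An internal review (IR) form was created to record the final determination on best overall response". Neither document says that the deciding person or team is kept unaware of treatment arm.

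**Whether the change is acknowledged.** On amendments, SAP 1.4.1 states: "There is no amendment". SAP 2.2.6 does flag another departure, in the patient-reported symptom model: "note a change from GEE model stated in the protocol". No such note accompanies the change in who determines response.

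**What is measured.** Protocol 10.1 states: "The technique(s) used for measurement of the tumor will be left to the discretion of the Investigator". The same sentence goes on to require that the technique or techniques stay the same within a patient. Protocol 10.2 and SAP 2.2.4 base response on physical measurement together with imaging. Protocol 11.1, 11.4 and 11.5 ask for the WHO measurements by mammography and ultrasound. A confirmatory assessment is deliberately not required.

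**How response is used.** SAP 2.2.6 compares objective response (CR or PR against everything else) between arms, with an exact 90% CI for the difference. Protocol 15.2 makes all secondary analyses descriptive, without multiplicity control.

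**The concern.** When an endpoint depends on a reader's judgement, its between-arm comparison is protected by three things: more than one reader, readers who do not know the arm, and a fixed rule for turning measurements into a category. The SAP names one reader where the protocol named three roles. The available text of neither document describes masking. Neither gives a rule for the case in which palpation, mammography and ultrasound put the same tumour in different WHO categories.

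What is at stake is the credibility of one reported efficacy contrast, the difference in objective response. A reader of the results would assume that the team promised in the protocol made the calls. As the SAP stands, that reader could not tell that it may not have done so, or whether the person who did knew the treatment.

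**Working it through.** **1. The texts on who decides, side by side.** The protocol names three roles in three places (synopsis, 4.2, 10.3). The SAP names one role in one place (2.2.4 item 5). There is no amendment (SAP 1.4.1). The SAP flags its change of model for patient-reported symptoms but not this change. The discrepancy is exact and unexplained.

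**2. Masking.** Neither document calls this trial open label in the available text, so that has to be inferred. Protocol 9.1 gives arm A as "Triptorelin 3.75 mg i.m. on day 1 of every cycle" and arm B as "Degarelix 240 mg s.c. given as two subcutaneous injections of 120 mg on day 1 of cycle 1". Route and number of injections differ, and no placebo or dummy injection is described. Treatment was therefore very probably known at the sites. Whether the central reviewer knew the arm is not stated.

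**3. Which measurement counts.**
- Protocol 10.1: the investigator's choice, held constant within a patient.
- Protocol 10.2 and SAP 2.2.4: caliper or ruler, and imaging.
- Protocol 11.1.6, 11.4.6 and 11.5.10: mammography and ultrasound.
- SAP 3.4: clinical, mammographic and ultrasound sizes all listed at baseline.

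Holding techniques constant settles consistency over time. It does not choose among three techniques that are all used at baseline, after cycle 3 and before surgery. The 50% and 25% thresholds apply only once a measurement has been chosen.

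**4. The plan's own figure.** No precision or power is stated for response, so there is nothing to reproduce there. The only design figure is 90% power with 23 per arm for the log-rank test on time to estradiol suppression. Simulation from the tabulated percentages gives 91.5% to 96.2% with 23 per arm, depending on how event times are placed between visits. With events placed at the visits or spread evenly between them, 21 to 22 per arm reach 90%. The stated figure is sound and slightly conservative. It rests on a centrally assayed hormone, so the identity of the response assessor does not enter it.

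**5. Size for response.** Inputs:
- 25 per arm (Protocol 15.1.1).
- Two-sided 90% interval, z = 1.645 (Protocol 15.2.4, SAP 2.2.6).
- Response rate 50%, an assumption taken from the letrozole plus GnRH analogue series in Protocol 3.3 (1 complete and 15 partial responses in 32 patients).

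Results:
- One reclassified patient: 1/25 = 4 points.
- Wald half-width: 1.645 × √(2 × 0.5 × 0.5 / 25) = 1.645 × 0.1414 = 0.233, about 23 points.
- At 70.4%, the higher response rate in the randomized goserelin study cited in Protocol 3.3: 1.645 × √(2 × 0.704 × 0.296 / 25) = 0.212, about 21 points.
- Two one-way calls: 8/23.3 = 34% of the half-width. Three: 12/23.3 = 52%.

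Starting from 12/25 in each arm, with Wald 90% intervals:

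| Reclassification | Difference (points) | 90% CI (points) |
|---|---|---|
| 2 in one arm | 8 | −15 to 31 |
| 3 in one arm | 12 | −11 to 35 |
| 5 in one arm | 20 | −2.5 to 42.5 |
| 6 in one arm | 24 | 1.9 to 46.1 |
| 3 in each arm, opposite directions | 24 | 1.4 to 46.6 |

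The SAP specifies an exact interval without naming the method. Under an unconditional exact interval ordered on the raw difference, a 24-point difference has a lower limit of about −1 point, so the last two rows would still include zero.

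**The case against.** The strongest reply is that the change in personnel does not create the exposure. The protocol's team was not described as masked either, and the protocol has the same gap on discordant measurements. A reader might infer that restoring the team would remove the bias; the documents do not support that. More readers would reduce idiosyncratic calls, but all three could know the arm. This objection stands, and it is why the fix has to include masking and a rule.

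A reader might also infer that one unmasked officer was free to pick among techniques. Protocol 10.1 gives the choice of technique to the site investigator and holds it constant within a patient. It restricts multifocal disease to the largest lesion, asks for the same measurer where possible and fixes the handling of very small diameters. The WHO thresholds for PR, SD and PD are numerical. What remains is narrower: no stated hierarchy when the recorded techniques disagree.

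A third tempting inference is a shift in the sponsor's favour. Nothing supports it. The sponsor is the cooperative group. The pharmaceutical partner's name is also attached to the triptorelin product whose safety data are cited in Protocol 12.3, so no one-sided interest is visible. Any bias could run toward either arm.

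Finally, the SAP sentence may be shorthand for the team process. If so, one clarifying sentence settles that part. Forgoing confirmation of response is a repeated protocol decision and is not criticised here.

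**Conclusion.** The concern holds in limited form. The protocol and SAP contradict each other on who determines best overall response, and the SAP does not flag it. With no described masking and no rule for discordant measurements, the response comparison is open to bias in either direction.

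The size is modest but not negligible: 4 points per reclassified patient against a half-width of about 23. Two one-way calls would not change the reading of the interval, and three would leave it inconclusive. From equal rates it takes about six one-way calls, or three in each arm in opposite directions, to reach the boundary of excluding zero, and whether zero is then excluded depends on the interval method. The documents do not show that any call was wrong.

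This rests on 25 per arm (51 patients were enrolled and the split is not given; with 26 in an arm one patient is 1/26 = 3.8 points), on an assumed response rate near 50%, and on the inference that treatment was open label. Part of the protocol, between sections 7.2 and 7.4, was not in the available text. The endpoint is secondary and descriptive, and a reader should not extend the point to the primary estradiol result.

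**What to change.** 1. Reconcile SAP 2.2.4 item 5 with Protocol 10.3. State who determined response and whether they knew the arm. If one person did it, flag the departure as the SAP does for its change of model.
2. Have the three roles already named in the protocol review a listing of measurements that omits treatment arm, and record on the internal review form that the review was masked.
3. Derive the WHO size-based category by program from the recorded diameters, separately for each technique. Before treatment arm is joined to the listing, name one technique as the main one. Report the others as sensitivity analyses, so that several response rates do not compete.
4. List every patient whose reviewed category differs from the programmed one. New lesions and complete disappearance of disease cannot be read from diameters alone and still need the reviewer's entry.

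The cost is a masked listing, some programming and a repeat review of about 50 cases. No new measurements or staff are needed. SAP wording alone is not enough if one person made the calls: the SAP describes the determination in the past tense, so restoring the team then means reviewing the cases again. A reviewer who has already seen cases with the arm known may not be fully masked the second time. That should be stated, and it is a further reason to report the programmed category beside the reviewed one.

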11.3. Day 1 of every treatment cycle

- 11.3.1. Physical examination, ECOG Performance Status, and body weight
- 11.3.2. Collection of any adverse event and assignment of appropriate adverse events grade according to the NCI CTCAE Version 4
- 11.3.3. Record all concomitant medication
- 11.3.4. Breast palpation with tumor measurement and nodal status (caliper or ruler measurements preferred)
- 11.3.5. For estradiol level determination by central laboratory (for primary trial endpoint): Take a blood sample **before the administration of the next dose of the GnRH agonist or antagonist**; extract serum and store at -80°C.
- 11.3.6. Local determination of estradiol level
- 11.3.7. The patient must complete a PRS questionnaire **on day 1 of cycles 2 and 4**

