13.1. Adverse event reporting

The main criterion for tolerability is the occurrence of toxicities and adverse events. The severity and causality will be classified according to the NCI CTCAE Version 4. The CTCAE is available for downloading on the internet at <http://evs.nci.nih.gov/ftp1/CTCAE/About.html>. An interactive version can be found at <http://safetyprofiler-ctep.nci.nih.gov/CTC/CTC.aspx>.

An adverse event is defined as any untoward medical occurrence that occurs from the first dose of study medication until 30 days after the final dose, regardless of whether it is considered related to a medication.

Symptoms of the targeted cancer (if applicable) should not be reported as adverse events.

An overdose, accidental or intentional, whether or not it is associated with an AE, of an investigational product should be reported as an SAE.

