13.2. Targeted adverse events

The presence or absence of any of the following adverse events will have to be indicated on each occasion that an Adverse Event Form (Form 41-AE) is completed.

Adverse events should be graded using the NCI CTCAE version 4.0. The following list provides targeted adverse events (ordered by System Organ Class) that should be recorded on the eCRF at any time. Treatments to alleviate these should be recorded on the 41-CCM Form:

Reproductive system and breast disorders:

Vaginal dryness

Dyspareunia

Psychiatric disorders:

Libido decreased

Depression

Anxiety

Insomnia

Renal and urinary disorders:

Urinary incontinence

Vascular disorders:

Hot flashes
Hypertension
Thromboembolic event

Musculoskeletal and connective tissue disorders:

Osteoporosis
Myalgia
Arthralgia

Injury, poisoning and procedural complications:

Fracture

Nervous system disorders:

Stroke
Transient ischemic attacks
Intracranial hemorrhage

Cardiac disorders:

Acute coronary syndrome
Myocardial infarction
Ventricular arrhythmia
Ventricular fibrillation

Gastrointestinal disorders:

Nausea

General disorders and administration site conditions:

Fatigue
Injection site reaction

Immune system disorders:

Allergic reaction

Metabolism and nutrition disorders:

Glucose Intolerance
Hyperglycemia

Investigations:

Aspartate aminotransferase (AST) increased
Alanine aminotransferase (ALT) increased
Blood bilirubin increased
Electrocardiogram QT corrected interval prolonged

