15.2. Secondary objectives

Secondary objectives include evaluation with respect to several secondary endpoints as defined in section 4.2. Analyses of the secondary endpoints will be descriptive. Tests of significance, whenever applicable, will not be controlled for multiple comparisons. Due to the limited sample size, the tests will largely be underpowered except in cases where differences between treatment groups are substantial. Randomized patients who received at least one dose of study treatment are included in the analysis unless otherwise indicated.

15.2.1. Tolerability (Safety of combined neoadjuvant therapy):

Tolerability will be evaluated in each treatment arm separately. Randomized patients who received at least one dose of the trial treatment will be included in the tolerability analyses.

The frequencies of adverse events (AE) according to CTCAE 4 by type and worst grade experienced while on the neoadjuvant treatments will be summarized and tabulated by treatment arms. Two-sided 90% confidence interval (CI) for the difference in proportion of patients with each type of grade 3 or higher targeted adverse event (see section 13.2) between the treatment arms will be assessed.

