 - Partial Response (PR): A 50% or more decrease in total tumor size (i.e. the product of the lesion's maximal diameter (MD) and the corresponding largest perpendicular diameter (LPD) of lesion) which have been measured to determine the effect of the therapy. In addition, there can be no appearance of new lesions or progression of any lesion;
 - Stable Disease (SD): Neither a 50% decrease in total tumor size (i.e. the product of the lesion's two diameters, MD*LPD of lesion) nor a 25% increase in the size of one or more measurable lesions has been determined;
 - Progressive Disease (PD): An increase of at least 25% in total tumor size relative to the smallest size measured during the trial and/or appearance of one or more new lesions.
6. Safety and tolerability: Adverse events (AE) were collected using CTCAE v4.0.
 - a. Each targeted AE will be classified according to the maximum grade of the event while on trial treatment (grade 0,1,2,3,4,5; where 0=no report).
 - b. Other grade 3-5 AEs will be classified according to the maximum grade of any reported other AE.
 7. Patient-reported symptoms (PRS) outcomes (see Section 2.2.6)

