 - Objective response (CR/PR as best overall response) rate was summarized as N (%) with 90% CI, overall and by treatment arm, as well as the absolute percent difference of objective responses between arms were reported with exact binominal 90%CI.
 - Clinical responses at the end of cycle 3 and 6, including complete response (CR), partial response (PR), stable disease (SD) and progressive disease (PD) were descriptively summarized by treatment arms.
- Safety and tolerability

Tolerability was evaluated in each treatment arm separately, using the safety population. For each patient, the targeted AEs recorded over time were summarized for each AE type as the maximum grade reported for that AE (without regard to reported relation to study treatments). The frequencies and percentages of patients experiencing each targeted AE were reported according to maximum grade, separately by treatment arm.. Two-sided 90% exact confidence interval (CI) for the difference in proportion of patients with each type of grade 3 or higher targeted AE between the treatment arms were assessed.

- The maximum grade of all targeted AEs are summarized by treatment arm, and the number and percentage of patients experiencing at least one grade 3 or higher targeted AE will be reported (with CI) according to treatment arm.
- Targeted adverse events (AEs) and other (non-targeted) grade 3 or higher AEs occurring during study were collected using CTCAE v4.0 on the AE Form. The AE Forms were submitted at the end of every cycle (27 days) and 30 days after surgery. All patients submitted AE data during 6 cycles of treatment period when available.
- AEs are reported as maximum grade. The maximum grade consolidates the reports of a given type of AE for a patient over time by taking the maximum

(worst grade) across time (i.e., a patient appears only once for a given type of AE). Patients with reports of multiple AEs of different types are reported multiple times under the relevant AE categories. Maximum grade 0 indicates that the AE type was not reported.

▪ Patient-reported symptoms (PRS) analysis

Longitudinal assessments collected PRS outcome at *baseline* (prior to randomization), at *day 1 of cycle 2 (day 29)*, at *day 1 of cycle 4 (day 85)* of triptorelin or degarelix administration and prior to surgery.

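### The protocol calls for any adverse event to be collected and tabulated, but the SAP covers only targeted events and other events of grade 3 or higher, so non-targeted grade 1-2 events drop out undeclared

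*SAP*

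**What the plan says.** **Protocol.** Section 13.1 defines an AE as "any untoward medical occurrence that occurs from the first dose of study medication until 30 days after the final dose", whether or not it is thought related to a medication. Section 11.3.2 requires, on day 1 of every cycle, "Collection of any adverse event and assignment of appropriate adverse events grade according to the NCI CTCAE Version 4". Sections 11.5.6 and 11.6.1 repeat the requirement before surgery and 30 days after it. Section 15.2.1 then plans the table: "The frequencies of adverse events (AE) according to CTCAE 4 by type and worst grade experienced while on the neoadjuvant treatments will be summarized", by arm. The next sentence limits only the 90% confidence interval, which is "for the difference in proportion of patients with each type of grade 3 or higher targeted adverse event". Section 13.2 introduces its list with "The following list provides targeted adverse events (ordered by System Organ Class) that should be recorded on the eCRF at any time". It makes those events compulsory on every AE form and does not say that other events are left out.

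**SAP.** Section 2.2.6 states: "Targeted adverse events (AEs) and other (non-targeted) grade 3 or higher AEs occurring during study were collected using CTCAE v4.0 on the AE Form". The frequency table by maximum grade is specified for each targeted AE. For the rest, section 2.2.4 item 6b says: "Other grade 3-5 AEs will be classified according to the maximum grade of any reported other AE". Section 1.4.1 records that the protocol was not amended.

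**The concern.** Both the scope of collection and the scope of tabulation are narrower in the SAP than in the protocol. With no amendment, the protocol text still governs. The SAP marks other departures openly: the confidence intervals not produced (2.2.5), the PEPI interval not done, and the move from GEE to a mixed model (both 2.2.6). A reader would therefore take the safety scope to be unchanged.

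What is at stake is the tolerability conclusion. Protocol 15.3 says that no safety data exist for this use of degarelix with letrozole in premenopausal women with invasive breast cancer. Tolerability is the first secondary endpoint listed in protocol 4.2. The degarelix reactions in protocol 12.1 come from trials in men, so a target list built on expected reactions may be incomplete for this population. An unqualified statement on tolerability would claim more than the SAP's tables examine.

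**Working it through.** The plan gives no figure on this point to reproduce. The check is a comparison of texts, then a count and an illustration.

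**Step 1. Scope side by side.**

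| Element | Protocol | SAP |
|---|---|---|
| Collection, targeted AEs | any grade (13.2, 11.3.2) | any grade (2.2.4 item 6a, 2.2.6) |
| Collection, non-targeted AEs | any grade (11.3.2, 11.5.6, 11.6.1) | grade 3 or higher only (2.2.6) |
| Frequency table | AEs by type and worst grade, by arm (15.2.1) | targeted AEs by maximum grade, by arm (2.2.6) |
| Between-arm 90% CI | grade 3+ targeted AEs (15.2.1) | grade 3+ targeted AEs (2.2.6) |

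The last row agrees. The conflict is confined to non-targeted AEs of grade 1-2.

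**Step 2. Which listed reactions are untargeted.** Compare the very common and common reactions in protocol 12.1 and 12.4 with the list in 13.2.

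- Degarelix: 18 listed. Seven are on the target list, counting musculoskeletal pain as myalgia or arthralgia. That leaves 18 - 7 = 11: anemia, weight increase, dizziness, headache, diarrhea, hyperhidrosis, rash, gynecomastia, chills, pyrexia and influenza-like illness.
- Letrozole: 21 listed, 8 targeted, 21 - 8 = 13 not targeted. Examples are constipation, dyspepsia, alopecia and edema.

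**Step 3. Chance of seeing at least one case in an arm.** Inputs: n = 25 per arm (protocol 15.1.1) and any-grade rate p. Protocol 12.1 gives 1-10% as the band for common reactions; using it here is an assumption. If all grades are recorded:

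P(at least one) = 1 - (1 - p)^25

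- p = 1%: 1 - 0.99^25 = 22.2%
- p = 5%: 1 - 0.95^25 = 72.3%
- p = 10%: 1 - 0.90^25 = 92.8%

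Under the SAP rule only the grade 3+ share s of cases is recorded. The documents do not give s, so a range is assumed:

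P(at least one recorded) = 1 - (1 - p × s)^25

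| p | all grades | s = 5% | s = 10% | s = 20% | s = 50% |
|---|---|---|---|---|---|
| 1% | 22.2% | 1.2% | 2.5% | 4.9% | 11.8% |
| 5% | 72.3% | 6.1% | 11.8% | 22.2% | 46.9% |
| 10% | 92.8% | 11.8% | 22.2% | 39.7% | 72.3% |

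For example, with p = 5% and s = 10%, 1 - 0.995^25 = 11.8%.

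**The case against.** The other side has a good deal to say, and most of it limits the size of the point.

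- **Other sources cover part of the gap.** FACT-ES has items on dizziness, headache, diarrhea, weight gain and cold or night sweats, and SAP 2.2.6 models individual items by arm and time. Protocol 16.1 itself suggests that physician grading can understate symptoms. A reader might infer that untargeted low-grade reactions would be invisible throughout the results; for these five that is not so. FACT-ES is self-reported at four time points and is not CTCAE-graded, so it does not replace the AE table. The items named in SAP 2.2.6 do not include rash, chills, pyrexia or influenza-like illness.
- **Low-grade anemia is a weak example.** Protocol 13.3 treats an abnormal laboratory value as an AE only from grade 3, with further conditions.
- **Serious events are reported whatever their grade** (protocol 13.4.3), and the DSMC reviews AEs every six months. Both stand, although the SAP specifies no SAE table.
- **Type may not be lost for other severe events.** Item 6b read alone could suggest that other grade 3-5 AEs collapse to one grade with no term. SAP 2.2.6 does not support that: it takes the maximum grade within each type of AE and counts a patient under every relevant category. Item 6b is ambiguous beside that text and needs rewording; it is not proof of a loss.
- **The restriction is in plain sight, and the data may not exist.** SAP 2.2.6 does say what the AE Form collected. If grade 1-2 non-targeted events were never captured, no table can recover them. This affects which remedy applies; the mismatch with the protocol remains.
- **The formal comparison is unchanged.** The between-arm interval matches the protocol, and secondary analyses are descriptive. Nothing here touches the primary endpoint.

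**Conclusion.** The discrepancy holds. Followed as written, the SAP omits part of a tabulation that the protocol promises, with no amendment and no declared change. The omitted part is the non-targeted AEs of grade 1-2.

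A reader might go further and infer that most non-targeted events go unreported. The documents do not support that, because none gives the share of these events that are grade 1-2. A majority is plausible but is not shown.

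The probabilities of 22%, 72% and 93% at rates of 1%, 5% and 10% are illustrations. They assume 25 independent patients per arm and any-grade rates spanning the band that protocol 12.1 reports from men; the grade split is unknown. The 93% belongs to the top of that band only. The clearest gap among the listed common degarelix reactions is rash, chills, pyrexia and influenza-like illness, which are neither targeted nor among the FACT-ES items named in the SAP. The point should be corrected because it bears on the tolerability statement for a combination with no earlier safety data in this setting.

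**What to change.** Reconcile SAP 2.2.4 item 6 and 2.2.6 with protocol 11.3.2, 11.5.6, 11.6.1 and 15.2.1.

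1. Establish whether the AE Form captured non-targeted grade 1-2 events.
2. If it did, add to SAP 2.2.6 a table of those events by term, worst grade and arm, as protocol 15.2.1 states.
3. If it did not, as SAP 2.2.6 suggests, declare this in the SAP as a deviation from the protocol. Restrict the tolerability conclusion to targeted AEs and AEs of grade 3 or higher.
4. In either case, reword item 6b so that other grade 3-5 AEs are reported by term, consistent with the handling of AE types in SAP 2.2.6.

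The cost is one or two descriptive tables from existing data, or a narrower tolerability statement. No new data, test or change in sample size is needed.
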